## 7. Study Design

This will be single-center, prospective, pilot, pre/post implementation study to collect post-market data on hospitalized subjects monitored via telemetry and surveillance monitoring.

Subjects who meet all of the inclusion criteria and none of the exclusion criteria will be assigned to either one of the monitoring groups and then followed for the duration of their hospital stay.

The subject population will include up to a total of 440 subjects with up to 220 subjects in each monitoring group.

### 7.1. Duration

The planned duration of the study is greater than or equal to six months. The control (TM) group will complete enrollment first over an estimated three month period, followed by an estimated three month enrollment period for the SM group.

Subject participation will last less than or equal to the duration of the hospital stay. Each subject will be followed in the hospital for a maximum period of 30 days ( $\pm$  2 days) from the start of enrollment.

No follow-up will occur after subjects are discharged from the hospital.

### 7.2. Rationale

The rationale for the study is fueled by: 1) reported widespread overuse of telemetry in US hospitals; 2) recommendations from the Choose Wisely campaign to reduce overutilization of resources; 3) recent advances in monitoring technology alternatives; 4) lack of prospective clinical evidence to support surveillance monitoring as an alternative to telemetry.

## 8. Product Description

### 8.1. Surveillance Monitoring System

#### 8.1.1. Vital Sync™ Informatics Manager (IM) & Virtual Patient Monitoring Platform (VPMP)

The Vital Sync™ Informatics Manager (IM) & Virtual Patient Monitoring Platform (VPMP) (Medtronic, Boulder) is a software only device that provides mobile and centralized remote monitoring. The Vital Sync™ IM is intended to route and store medical device data from connected medical devices to the electronic medical record (eMR), clinical information system (CIS) and/or the VPMP. The Vital Sync™ VPMP displays information received from the IM on any web-enabled device. The product is a Class II device and 510(k) cleared by the FDA.

The Vital Sync™ IM & VPMP routes and displays parameters, waveforms and alarms for the connected medical devices in near-real time. The Vital Sync™ IM & VPMP allows users to set up a new default alarm priority across device types and allows for institutions to modify alarm priorities per their internal protocols. The Vital Sync™ IM & VPMP provides for the setting or adjusting of thresholds on supported

This document is electronically controlled. Printed copies are considered uncontrolled.

**Confidential**

Protocol #: COVMOPO0561

Rev E 09AUG2017

devices where this capability is not available on the device itself; the platform can also act as the primary display for patient data and alerts where this capability is not available or enabled on the device itself. Vital Sync™ IM & VPMP includes Turn Time functionality which allows position and posture of the patient to be monitored. The Vital Sync™ IM & VPMP allows the user the capability, via the software, to perform simple calculations from processed parameters, or from manual input by the user.

The Vital Sync™ IM & VPMP will receive and display vital sign data from the BioModule wearable physiological monitor (see Section 8.1.2).

The indications for use are as follows:

The Vital Sync™ IM is software that is intended to route and store medical device data and device diagnostic information from supported devices to the VPMP, 3rd Party Annunciation Systems, Electronic Medical Record (eMR) and Clinical Information System (CIS).

The Vital Sync™ VPMP is a display system that provides visual and audible renderings of physiologic data, waveforms, alarms and alerts routed through the Vital Sync™ IM from supported devices. The Vital Sync™ VPMP is intended to be used by healthcare professionals in a hospital or hospital-type facility for the following purposes:

- To remotely view and review patient data, waveforms, alerts and alarm information from supported devices and clinical information systems to facilitate clinical management.
- To facilitate remote collaboration with other healthcare professionals regarding patient data from supported devices.
- To access additional processed parameters to facilitate patient monitoring, assessment and clinical management.
- To set and adjust alert thresholds on supported devices where this capability is not available on the device itself.
- To access data, waveforms and alerts from supported devices where these capabilities are not enabled or available on the device itself.

**WARNING:** The Vital Sync™ IM & VPMP is a notification system and is not a replacement for direct patient observation, patient assessment or clinical judgment.

### 8.1.2. Wearable Physiological Monitor

The BioModule™ BH3-M2 sensor is a wearable physiological monitoring device intended for monitoring adults in hospitals and alternate care settings. When combined with the BioModule Holder and snap ECG electrodes, it becomes the BioPatch™ wireless device. It continuously collects a patient's physiologic data including ECG, HR, RR, body orientation, and activity and transmits data to the Vital Sync™ VPMP every [REDACTED]. The BioModule™ sensor provides a [REDACTED], single-lead ECG that records either automatically or on demand when a patient's heart or respiration rate crosses clinician-assigned thresholds.

The BioModule™ sensor is a Class II device and 510(k) cleared by the FDA.

[figure not shown]
BioModule™

This document is electronically controlled. Printed copies are considered uncontrolled.

**Confidential**

Protocol #: COVMOPO0561

[REDACTED] Rev E 09AUG2017 [REDACTED]

[REDACTED]

- [REDACTED]
- [REDACTED]
- [REDACTED]
- [REDACTED]
- [REDACTED]
- [REDACTED]
- [REDACTED]
- [REDACTED]
- [REDACTED]
- [REDACTED]

## 8.2. Packaging

Research conducted for this study will utilize devices cleared through the 510(k) regulatory process. FDA cleared devices do not require special labeling. Labeling and package for all products used in this study will follow the local and regional regulatory requirements. Labeling, user guides, and instructions for use will be provided to the site.

## 8.3. Intended Population

The intended study population is adult patients hospitalized and scheduled for telemetry monitoring but do not meet AHA criteria for telemetry monitoring.

## 8.4. Product Use

The Vital Sync™ IM & VPMP will be used to allow clinicians to remotely view patient information collected from the BioModule and enable clinicians to be notified of clinical distress via color coded alarms and audible alerts. The BioModule will be attached to each subject and placed on the lower section of the sternum via two electrodes.

User guides and instructions for use of the Vital Sync™ IM & VPMP and BioModule™ will be provided to the study team prior to or at the Site Initiation Visit.

This document is electronically controlled. Printed copies are considered uncontrolled.

## 8.5. Product Training Requirements

Prior to investigation site activation or subsequent involvement in clinical study activities, Medtronic will provide product and clinical study training relevant and pertinent to the involvement of personnel conducting clinical study activities and investigator responsibilities.

As a minimum, Investigators and coordinators will be trained on their responsibilities, on the CIP, on the use of data collection tools as well as applicable local regulations. Study-specific training will be documented prior to investigation site activation. Hospital staff will be trained on the surveillance monitoring system prior to start of the SM phase of the study.

The support and training of the hospital units using the study product will be performed by employees of Medtronic.

## 8.6. Product Receipt and Tracking

The following records will be maintained at minimum for product delivery, receipt and tracking at the site: dates, quantities received, lot/serial numbers, and expiration dates, as applicable. Traceability of devices will be achieved during and after the clinical investigation by means of recording lot numbers, batch numbers or serial numbers, as applicable, on the Product Accountability Log (PAL). There are no investigational devices/supplies being utilized in this study. All non-investigational devices/supplies associated with Vital Sync™ IM & VPMP and the BioModule will be maintained on the PAL as instructed during the Site Initiation Visit training.

## 8.7. Product Return

The investigator will return used and unused study supplies and maintain documentation of return as instructed during the Site Initiation Visit training. Study supplies should be returned to: [REDACTED]

## 8.8. Product Storage and Accountability

The investigator will store the study product per the instructions for use and product manual. The storage area should be locked/secure with access limited only to approved hospital and study staff. Devices should be stored in a way that they will not be mixed with standard clinical inventory.

Use of the study devices by each participant will be recorded on the PAL as instructed during the Site Initiation Visit training.

## 8.9. Recalls

In the event of a recall, Medtronic will immediately inform investigator to cease the use of the product or other study equipment and make arrangements for the return/disposition of the recalled product.

Medtronic will notify the FDA and all reviewing IRBs/ECs, within 30 working days after the request is made to cease the use of the device, as applicable.

This document is electronically controlled. Printed copies are considered uncontrolled.

**Confidential**

Protocol #: COVMOPO0561

[REDACTED] Rev E 09AUG2017  
[REDACTED]

## 9. Selection of Subjects

### 9.1. Study Population

The target population consists of hospitalized patients aged  $\geq 18$  who are scheduled for admission to telemetry but do not meet AHA criteria for telemetry.

### 9.2. Subject Enrollment

Subject is considered enrolled once they sign the informed consent form. Subject will be considered a screen failure and immediately exited from the study if:

- The subject signs the informed consent form but fails to meet study inclusion/exclusion criteria.
- The subject signs the informed consent form, meets the study inclusion/exclusion criteria but does not start telemetry or surveillance monitoring for any reason.

The investigator will maintain a log of all subjects enrolled in the clinical investigation called the Subject Identification Log for internal use to track subject identification numbers, subject names, and contact information. This log will be kept updated in real time during enrollment and stored in the ISF.

A Screening and Enrollment Log described in Section 10.3 will also be maintained by the investigator.

Individual subject enrollment will be complete when the subject is discharged from the hospital, completes 30 days ( $\pm 2$  days) of enrollment, or is withdrawn from the study, whichever comes first.

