### 10.2.1. Screening/Enrollment Visit

The first visit is the screening and enrollment visit. Patients considered potential candidates for the study based on pre-screening will sign informed consent form prior to participating in any study activities.

The following procedures and assessments will be performed **during both phases of the study** on the day of study enrollment and the results will be recorded on the subject eCRFs.

- Signed and dated informed consent
- Pregnancy test if applicable
- Verify that the subject meets all inclusion/exclusion criteria and collect the following:
  - Demographics
  - Medical history
  - Hospital admission data
- Assignment to monitoring group
- Assignment of study number
  - SM group will be a consecutive number beginning with 1001
  - TM group will be a consecutive number beginning with 2001
- Verify data and enter into eCRF within 5 preferred business days of collection

**During the TM Phase only**, the following procedures and assessments will be performed.

- Eligible clinicians complete Telemetry Utilization Questionnaire for Clinicians (PRE)
- Eligible clinicians complete Perception Questionnaire for Prescribing Clinicians (PRE)

**During the SM Phase only**, the following procedures and assessments will be performed.

- Attach BioModule to subject according to user manual instructions and keep device attached to subject for the duration of the evaluation or until fully charged BioModule is needed
- Link subject to BioModule using the Vital Sync™ VPMP
- Confirm that BioModule is communicating to Vital Sync™ VPMP by observing flashing green light on BioModule AND that HR, RR, and activity parameters are displayed on the central station

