#### **10.6. Randomization**

No randomization will be used during the course of the study. Assignment to a monitoring arm will be determined by the phase status of the study. During the TM phase, all subjects will be assigned to the TM group. During the SM phase, all subjects will be assigned to the SM group.

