## 10.10. Subject Withdrawal or Discontinuation

During the course of this study, subjects may elect to be or may be withdrawn from further treatment for any of the following reasons:

- The subject may withdraw from the study for any reason without prejudice
- The clinician or investigator may terminate the study at their discretion
- Subject is prescribed additional continuous monitoring after enrollment
- Within the first 12 hours of study participation, subject is discharged from hospital or removed from the study for any reason
- Subject no longer meet study inclusion/exclusion criteria
- Technical issues that prevent continuous data collection from the Vital Sync™ IM & VPMP
- Sponsor terminates the study
- Other

Subjects may withdraw from the study at any time and for any reason. If a subject officially withdraws from the study, the investigator will document the reason and collect final outcomes data from the subject's medical record. No additional follow-up will occur for withdrawn subjects.

Subjects may only be replaced if they are a screen failure OR are withdrawn from the study during the first 12 hours of enrollment for any reason.

Withdrawal or discontinuation from the study will not affect the subject's regular care/hospitalization in any way.

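### Eligible, consented subjects who never start monitoring are exited as screen failures and may be replaced, so their length of stay is in effect lost after assignment by phase, with a bias of unknown direction

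*Protocol*

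**What the plan says.** Protocol 9.2 sets enrollment at consent: "Subject is considered enrolled once they sign the informed consent form". It continues: "Subject will be considered a screen failure and immediately exited from the study if" either of two conditions applies. One is failing the eligibility criteria. The other is a consented subject who "meets the study inclusion/exclusion criteria but does not start telemetry or surveillance monitoring for any reason".

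Group membership needs no further step, because the phase decides it. Protocol 10.6 states "During the SM phase, all subjects will be assigned to the SM group", with the matching rule for TM.

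Protocol 10.10 governs what happens next. On replacement: "Subjects may only be replaced if they are a screen failure OR are withdrawn from the study during the first 12 hours of enrollment". On outcomes: "If a subject officially withdraws from the study, the investigator will document the reason and collect final outcomes data" from the medical record, which SAP 7.4 repeats. Neither document says the same for screen failures.

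Protocol 13.1 places screen failures with withdrawals in the attrition between 220 recruited and 132 needed per group. The primary analysis (Protocol 13.3, SAP 7.1.3) uses the evaluable data, and neither document defines that term. No analysis set is described that would bring non-starters back.

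**The concern.** These subjects have consented, passed every criterion and belong to a group by phase. Removing them because monitoring did not begin is an exclusion after assignment, and the reasons for not beginning need not be alike in the two phases.

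- **TM:** the telemetry has already been ordered and is the site's standard care (Protocol 10.1, 10.3).
- **SM:** the subject needs a place on a dedicated medical-surgical unit (Synopsis, 10.1), attachment of the sensor and linking to the platform. The enrollment visit also includes a check: "Confirm that BioModule is communicating to Vital Sync™ VPMP by observing flashing green light on BioModule" (10.2.1). Protocol 11.1 itself names radio interference and network failure as risks.

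The study is described as a pre/post implementation study, so whether a strategy can be started is part of the question. If non-starters differ in LOS from starters, and their number or type differs by phase, the SM/TM ratio among starters differs from the ratio among all eligible subjects. Without LOS on the non-starters, nobody can check by how much.

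**Working it through.** **1. Is LOS lost?** Four provisions bear on it. The subject is exited immediately (9.2). Outcomes are collected only after an official withdrawal (10.10, SAP 7.4). Screen failures are attrition in the sample-size reasoning (13.1). The Screening and Enrollment Log keeps reasons for non-participation, not outcomes (10.3). Because evaluable is undefined, the loss is an inference, but all four provisions point the same way.

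**2. The plan's own figure.** Inputs from Protocol 13.1 and SAP 6: coefficient of variation 0.65, margin 0.2 on the mean ratio (upper bound 1.20), true ratio 1, power above 80%, alpha 0.05.

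- Log-scale variance: ln(1 + 0.65²) = 0.3524, so SD = 0.594.
- n per group = 2 × (1.645 + 0.842)² × 0.3524 / (ln 1.2)² ≈ 131.1, rounded up to 132.

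The 132 reproduces with one-sided alpha 0.05. It is not in dispute here.

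**3. Size of the possible bias.** The documents give neither a non-start rate nor the LOS of non-starters, so both are assumed. Let f be the share of eligible SM subjects who do not start and k their LOS relative to SM starters. Assume log-normal LOS, no non-starts in TM, replacement so that 132 per group are analyzed, and a true ratio of exactly 1.20 among all eligible subjects.

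- SE of the log ratio = √(2 × 0.3524 / 132) = 0.0731.
- Log ratio among starters = ln 1.20 − f × ln k.
- Probability of declaring non-inferiority = Φ(f × ln k / SE − z).

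Example, f = 0.05 and k = 1.5: 0.05 × 0.4055 / 0.0731 = 0.277; Φ(0.277 − 1.645) = 8.6%.

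| f | k | Ratio among starters | False non-inferiority, one-sided 0.05 | One-sided 0.025 |
|---|---|---|---|---|
| 0 | any | 1.20 | 5% | 2.5% |
| 5% | 1.5 | 1.18 | 8.6% | 4.6% |
| 10% | 1.25 | 1.17 | 9.0% | 4.9% |
| 10% | 1.5 | 1.15 | 13.8% | 8.0% |
| 10% | 0.75 | 1.24 | about 2% | about 0.9% |

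The last row stands for subjects with short stays, such as those discharged before monitoring begins. If TM loses the same share with the same relative stay, f × ln k is subtracted from both group means, the ratio stays at 1.20 and the error stays at 5%. If only TM loses long-stay subjects, the sign reverses and the bias works against non-inferiority.

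**The case against.** Much can be said for the plan, and parts of it stand.

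- **Which subjects the rule catches.** Section 9.2 speaks of telemetry or surveillance monitoring, not of the monitoring assigned. A reader might infer that an SM-phase subject put on telemetry instead is dropped, but that subject has started telemetry and the wording does not clearly apply. If worsening brings a Class I or II indication, exclusion criterion 3 applies, which is ordinary ineligibility.
- **Device failures.** A reader might infer that every sensor that will not link removes a subject. Section 10.10 lists technical problems with platform data collection as a withdrawal reason, and outcomes are collected after withdrawal. Starting is not defined, so attaching the sensor may already count.
- **Telemetry delays.** Delay is not the same as never starting. That endpoint compares periods (6.1.2), and resource data come separately from hospital and billing records (10.2). The documents do not show that it loses subjects.
- **Label.** The plan does not say that non-starters fail eligibility; the bullet says they meet it. Only the screen-failure label is shared, and reasons are logged.
- **Design.** There is no randomization to break, and SM already requires the treating provider's agreement (criterion 6), which TM does not. Comparing subjects actually monitored is a legitimate target for a post-market pilot.
- **The remedy has its own risk.** SM non-starters may receive usual care. With a ratio of 1.20 among starters and 10% non-starters whose stay is like TM, the all-eligible ratio is exp(0.9 × ln 1.2) ≈ 1.18. Non-inferiority is then declared with probability Φ(0.1 × 0.1823 / 0.0731 − 1.645) ≈ 8%.

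The last point defeats any proposal to make the all-eligible set the sole primary set. None of the points explains why LOS should go uncollected for eligible subjects whose stay is already in the hospital record.

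**Conclusion.** The point holds and should be corrected. Read as written, the plan removes eligible, consented subjects after their group is fixed, allows their replacement, and provides no LOS for them.

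The stronger reading, that the rule hides SM failures and tilts the study towards non-inferiority, is not supported. The increase to between 8.6% and 13.8% depends on non-starts confined to SM, at 5% to 10%, with stays 1.5 times as long. Shorter stays lower the error, and equal loss in both groups leaves it at 5%. The attrition allowance of at least 30% in Protocol 13.1 mixes withdrawals and screen failures, so it does not supply a non-start rate. What can be said is that an avoidable exclusion introduces a bias that the planned data could neither size nor sign.

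**What to change.** In Protocol 9.2, 10.10 and 13.3 and SAP 7.1.1, 7.1.3 and 7.4:

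1. Restrict screen failure to subjects who fail inclusion or exclusion criteria.
2. Keep eligible consented non-starters in the group of the current phase and do not replace them. Collect their LOS, transfers and events from the medical and billing records.
3. State what counts as started in each phase, including how an SM-phase subject who goes on telemetry is classed, and define evaluable.
4. Report non-starts by phase and reason.
5. Analyze LOS in the all-eligible set by phase and in the monitoring-started set, and require non-inferiority to be shown consistently in both.

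The cost is wording in both documents and record abstraction for a few more subjects; Protocol 10.4 already expects the consent form to cover release of billing data. The all-eligible set will carry some dilution from subjects who never received SM, which is why both sets are needed. The 132 per group need not change on this account.

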### 9.3. Inclusion Criteria

Each subject must meet the following criteria to be enrolled in the study:

1. Signed and dated informed consent by subject
2. Male or female 18 years of age or older
3. Expected hospitalized admission on the general care floor or medical surgical unit for at least one overnight stay and/or  $> 12$  hours
4. Scheduled for telemetry monitoring
5. Diagnosis indicates AHA telemetry Class III or none and therefore not indicated for telemetry monitoring
6. For SM group subjects, treating provider who scheduled subject for telemetry agrees to alternative monitoring plan of surveillance monitoring
7. Willingness to have study devices attached and hair shaved at sensor location as needed during study participation
8. Willingness to participate in all aspects of the study

